### Dog Six-Cycle Repeat-Dose Toxicology Study

The objectives of this GLP-compliant study were to evaluate the potential toxicity and toxicokinetic profile of MLN8237 when administered to beagle dogs QD via oral gavage for a total of 6 cycles (each cycle consisting of daily dosing for 21 consecutive days; cycles were separated by a 7-day non-dosing period), as well as to evaluate the recovery, persistence, or progression of any effects during a minimum 28-day recovery period. [49] Administration of MLN8237 to beagle dogs QD via oral gavage at a dosage of 1.0 mg/kg for up to 6 days was not tolerated and resulted in lethality and dose reduction to 0.75 mg/kg for the surviving 4 animals for the remainder of the dosing period. Cyclical administration of MLN8237 to beagle dogs QD via oral gavage for the following 5 complete cycles, was well tolerated at a dosage of 0.75 mg/kg. Cyclical administration of MLN8237 to beagle dogs QD via oral gavage for a total of 6 cycles (each cycle consisting of daily dosing for 21 consecutive days with cycles separated by a 7-day nondosing period) was welltolerated at dosages of 0.45 and 0.15 mg/kg. Test article-related effects were limited to hematology and microscopic findings, all of which were consistent with outcomes associated with Aurora A kinase inhibition and were similar to what was noted in the 2-cycle repeat-dose toxicology study. The microscopic findings in the 0.45- and 1.0/0.75-mg/kg groups had completely resolved at the recovery necropsy, and the hematology findings had partially resolved in the 1.0/0.75-mg/kg group at the recovery necropsy.

### 2.1.4 Clinical Experience

There have been multiple company-sponsored clinical studies of alisertib (MLN8237) that are either ongoing or have completed enrollment. The solubility of MLN8237 molecules is low in acidic pH; hence, the drug was originally developed as the buffered PIC formulation for the initial phase 1 clinical studies. Subsequently, the ECT formulation was developed and has been evaluated in multiple studies.

Initial studies enrolled patients with advanced solid tumors. The major goals of each study were to evaluate safety, pharmacokinetics, and pharmacodynamics, and to determine the DLT(s) and MTD of alisertib (MLN8237) when administered for 7 consecutive days, followed by a 14-day

recovery period. The studies also included cohorts to evaluate longer dosing periods up to 14 or 21 days. In the first-in-human study phase I study conducted in the United States, 65 patients received MLN8237 across dose cohorts evaluating various dose levels and schedules with the PIC formulation. 65 pts received 5-150 mg QD for 7 days or 25-70 mg QD for 14 or 21 days. In addition, to minimize  $C_{max}$ -associated somnolence risk, divided treatments were given up to maximum administered doses 60 mg BID for 7 days or 40 mg BID for 14 days. Tumors were colorectal (14), lung (13), ovary (6), head and neck (6), prostate (4), and others (22). Dose limiting toxicities included grades 3-4 neutropenic fever (n=4), thrombopenia (n=3), somnolence (n=2), and mucositis (n=1), seen at doses  $\geq$  110 mg/d x 7 days,  $\geq$  40 mg BID x 14 days, and in 1 of 11 pts at 50 mg BID x 7 days. Most common adverse events included nausea (57%), diarrhea (52%), fatigue (48%), and alopecia (35%). The recommended phase 2 dose was 50 mg BID for 7 days. Durable partials response was documented in one patient with platinum-refractory ovarian cancer and treatment was for over 1.5 years ( $\geq$  30 cycles). Eight patients continued treatment for  $\geq$  6 cycles with stable disease. Alisertib (MLN8237) was deemed to be generally well tolerated.[50]

Concurrent with the above study, data was presented on pharmacokinetic and pharmacodynamic results from two phase 1 studies of alisertib (MLN8237) in patients with advanced solid tumors. In 117 patients who took MLN8237, the drug was absorbed rapidly (median  $T_{max}$ , 2h), steady-state exposures were achieved by 7 days and were dose-proportional over dosing ranges of 5-200mg per day. The recommended phase II dose 50mg BID  $\times$  7 days produced steady-state average concentrations (geometric mean  $\sim 1.7 \mu M$ ), exceeding the efficacious concentration estimated preclinically (1 $\mu M$ ). Mean  $t_{1/2}$  was  $\sim 21 h$ . At steady-state exposures, skin mitotic and apoptotic indices and tumor mitotic index increased, and tumor mitotic cell chromosome alignment and spindle bipolarity decreased, all demonstrating AAK inhibition. In evaluable pts with paired tumor biopsies, exposure-related changes were observed by D7, including decreases in chromosome alignment and spindle bipolarity.[51]

Another phase I trial of enteric coated (ECT) alisertib in advanced solid tumors was presented in the last year. The agent was administered orally BID for 7 days, followed by 14 days of rest, in 21-day cycles. 17 pts were treated, with frequent tumor types including sarcoma (n=4), and ovarian (n=2). The MTD was identified as 50 mg BID, with a DLT of Grade 4 febrile neutropenia was reported at 50 mg BID. The most common adverse events were neutropenia (47%) and fatigue (47%), and the most common grade $\geq$ 3 adverse event was neutropenia (41%), which was reversible. Following oral administration, MLN8237 ECT was absorbed at a moderate rate with an overall median  $T_{max}$  of 3 h and with dose-related increase in exposure over ranges of 10–50 mg BID. Mean  $t_{1/2}$  was  $\sim$ 20 h following multiple dosing, consistent with previous results.[52]

Alisertib has also been studied in solid tumor phase II trials as single agent and in combination.[54, 55] A study in combination with paclitaxel in a phase I/II trial of advanced solid tumor malignancies reported grade 4 diarrhea, grade 3 stomatitis (both at paclitaxel 80 mg/m^2 with

alisertib 20 mg BID) and grade 4 neutropenic fever (at paclitaxel 60 mg/m² with alisertib 30 mg BID). A MTD was not reached. Most common adverse events were neutropenia (n=18), anemia (n=13) and nausea (n=12). 21 pts had grade  $\geq$ 3 drug-related adverse events, with the most common being neutropenia (n=15). Eight patients experienced partial responses by RECIST and/or CA125 levels, and three patients had stable disease for  $\geq$  6 months.[55]

## 2.1.4.1 Clinical Studies in Hematologic Malignancies

Alisertib has also been studied in hematologic malignancies, with promising results. A phase 1 study of advanced hematologic malignancies was conducted across 6 dose cohorts, evaluating the following dose levels and schedules, initially using the PIC formulation of alisertib (initial cohort size n = 2-7): 25mg, 35 mg QD x 21 days; and 35, 45, 65, and 90 mg QD x14 days. With the 14day schedule, the MTD of alisertib (PIC formulation) was determined to be 45 mg QD in adult patients with advanced hematologic malignancies, established following occurrence of DLTs in four patients at higher dose levels: grade 4 thrombocytopenia, grade 4 neutropenia (65 mg QD); grade 3 febrile neutropenia, grade 4 thrombocytopenia (90 mg QD). The study was amended and expanded to evaluate the ECT formulation of alisertib administered BID with a 7-day schedule, specifically to characterize safety and pharmacokinetics with this formulation. The MTD for the ECT formulation was established as 50 mg BID, with four DLTs observed in three patients: at 40 mg QD for 14 days, one patient had grade 4 febrile neutropenia, and one patient had grade 4 bullous dermatitis and grade 4 neutropenia; at 50 mg BID for 7 days, one of nine patients had grade 4 neutropenia. In total, 55 patients were included (PIC n=28, ECT n=27). 60% of patients had non-Hodgkin's lymphoma, 35% multiple myeloma, and 5% chronic lymphocytic leukemia/small lymphocytic lymphoma. The most common drug-related adverse events (AEs) were neutropenia (PIC 46%, ECT 63%), thrombocytopenia (39%, 41%), and diarrhea (29%, 41%). 24 patients (PIC n=12, ECT n=12) had serious adverse events; the most common was febrile neutropenia (PIC n=1, ECT n=4). Tolerability appeared similar between the PIC and ECT formulations. Six patients (PIC n=3, ECT n=3) died during the study, but no deaths were considered related to alisertib. In the 42 evaluable patients, five (PIC n=3, ECT n=2) had partial responses, and 11 had a best response of stable disease (PIC n=6, ECT n=5). 26 patients had progressive disease (PIC n=14, ECT n=12).[56]

In a phase II trial of single agent alisertib in aggressive B-cell and T-cell non-Hodgkin lymphomas, patients were treated at a dose of 50mg twice daily for 7 days on 21 day cycles. 48 patients were enrolled, of whom 41 were evaluable for response. Most common Grade 3/4 adverse events were neutropenia (63%), thrombocytopenia (31%), stomatitis (15%), febrile neutropenia (13%) and fatigue (6%). The overall response rate (ORR) was 32%, with response by histology being 20% for DLBCL, 23% for MCL 23% and 57% for T- cell NHL. The investigators concluded that the generally manageable toxicity profile suggested an opportunity to combine alisertib with other agents [57]

At our institution, we have just finished accrual on a phase I, 3+3 cohort dose-escalation study of alisertib combined with standard 7+3 induction for newly diagnosed AML. We recently presented our data at the oral session during the 2014 American Society of Hematology Conference. For this study, those with acute promyelocytic leukemia or with AML and core-binding factor alterations were excluded. All patients received 7+3 induction (continuous infusion cytarabine 100mg/m^2 x 7 days and intravenous idarubicin 12mg/m^2 x 3 days), after which on day 8, alisertib was administered twice daily (BID) for 7 days. Dose escalation occurred via three cohorts (10mg BID, 20mg BID, 30mg BID). All underwent a mid-induction bone marrow biopsy, following course of alisertib, to assess for residual disease, which if present, was to be treated with 5+2 re-induction (cytarabine 100mg/m^2 x 5 days, idarubicin 12mg/m^2 x 2 days) without alisertib. Following induction, up to four cycles of consolidation were allowed, using cytarabine (3g/m^2 BID days 1,3,5 for those aged <60 and  $2g/m^2$  daily days 1-5 for those aged  $\ge60$ ) followed by alisertib, according to dose cohort, on days 6-12. After consolidation, alisertib maintenance was initiated, at cohort dose level, for days 1-7 of 21 day cycles, to be continued for 12 months or until disease progression. Those eligible for stem cell transplant (SCT), following induction and/or consolidation courses, were removed from study for this purpose.

Data on 16 patients were presented (n=3, 10mg BID; n=7, 20mg BID; n=6, 30mg BID). One patient (6%) had therapy-related AML and six (38%) had antecedent MDS or myeloproliferative neoplasm. Eleven of the 16 patients (69%) had high risk disease, as per older age (age over 65), high risk cytogenetics, and /or derived from preceding myeloid malignancy. *FLT3* mutations were detected in 3 (19%), *NPM1* mutations in 3 (19%), *CEBPA* mutations in 2 (13%), and *IDH1/IDH2* mutations in 6 patients (38%). One patient in cohort 2 died of sepsis, deemed unrelated to study drug, prior to completion of the toxicity assessment period and was replaced. Six (38%) patients have gone on to SCT. All patients received induction, and 9 patients received at least one cycle of consolidation, and 3 patients started maintenance therapy. Alisertib was well tolerated. All patients experienced expected grade 4 toxicities of anemia, thrombocytopenia, and febrile

## 2.2 Study Disease: Acute Myeloid Leukemia (AML)

AML is characterized by an arrest in differentiation and uncontrolled proliferation of myeloid precursors in the bone marrow. This underlying process frequently leads to hematopoietic insufficiency, and when undifferentiated cells escape the marrow, to significant leukocytosis, with often devastating and life-threatening sequelae. Unfortunately, successful treatment of AML remains a difficult challenge. Although the majority of adults under age 60 with de novo AML achieve a complete remission (CR) with traditional anthracycline and cytarabine based induction regimens, the long-term survival rates continue to be poor at approximately 30-40%. [60, 61] Remission rates and prognosis are significantly poorer for patients with high-risk AML, which includes older patients, those with poor-risk cytogenetic features, and those whose disease has arisen from myelodysplastic syndromes (MDS), myeloproliferative disorders (MPD), as well as those with secondary AML from environmental exposures or prior chemotherapy. In such cases, a remission is achieved in less than 40% of cases, with very poor long-term survival rates of less than 10%.[61, 62]

Anthracyclines and cytarabine have been the primary agents used for AML induction therapy for more than two decades. Early Cancer and Leukemia Group B (CALG-B) studies established the utility of these agents in induction regimens.[63] CALGB-7421 later demonstrated that induction with 7 days of cytarabine and 3 days of anthracycline (7+3) was superior to 5 days of cytarabine and 2 days of anthracycline (5+2).[64] Increasing the intensity of the regimen by extending the infusion of cytarabine to 10 days was also investigated, and was shown to have no impact in complete remission rate. Since that time, 7+3 has been extensively used as first line induction

Protocol Version Date: 5/18/2017

regimens in AML, although outcomes continue be frequently inadequate and poor, especially in older patients and those with high risk AML.[61]

Therefore, there is an urgent need for the development of novel approaches in the treatment of AML to improve outcomes for patients, especially those with high-risk disease. In the last few years, a variety of targeted and novel therapies have been combined with standard induction therapy, with some promising initial results[65-67], although the majority of advanced phase studies to date have failed to show an advantage in outcomes with combination therapies.

#### 2.3 Rationale

As mentioned above, there is a pressing need to develop novel approaches to the treatment of AML. Aurora kinases are a family of oncogenic serine-threonine kinases that regulate multiple phases of the mitotic signaling cascade. Inhibition of aurora A kinase (AAK) leads to mitotic errors, followed by aneuploidy, apoptosis, and senescence, which maybe especially applicable to cells recently or concurrently exposed to cytotoxic chemotherapy. Alisertib, also known as MLN8237, is an ATP-competitive, orally available inhibitor of AAK, which has been evaluated for safety and efficacy in Phase I and II trials of hematological malignancies including AML. [58] Recently, we have concluded a phase I study of alisertib in combination with "7+3" conventional induction chemotherapy, and found this combination to be safe and well-tolerated. In addition, there was a strong suggestion of efficacy with a significantly less than expected need for "5+2" reinduction and a significantly higher than expected rate of remission. Of note, the majority of patients on this study harbored high risk disease, as defined by age, preceding marrow disease, and cytogenetic risk. [59] The next logical step in establishing the efficacy of alisertib in combination with standard induction chemotherapy in patients with higher risk AML, who have particularly poor outcomes with standard therapies.

This protocol therefore describes a phase II clinical trial of alisertib, at a dose of 30 mg twice daily, combined with induction chemotherapy (7+3 cytarabine- and idarubicin

-based therapy) for patients with higher risk AML. 30mg twice daily is the RP2D based on a recently completed dose-escalation study of this combination. This will be a highly translational project, encouraged by laboratory investigation of AAK activity in myeloid malignancies and promising recent clinical data mentioned above, and will be informed by correlative studies assessing in vivo pharmacodynamic parameters.

#### 2.4 Correlative Studies

We will perform gene panel sequencing on bone marrow aspirate and/or blood samples collected at baseline, day 14 of induction (range 13-16), count recovery following induction (range 35-45, 55-65 if re-induction given), and at any time of relapse or suspicion of relapse. All samples will be processed in a CLIA certified lab. De-identified samples obtained from blood, bone marrow, and skin biopsies from selected cases will be subjected to broader sequence analysis (whole exome

or genome). These exploratory analyses will be performed with several hypotheses in mind. First, we will evaluate whether a specific mutational profile is associated with treatment response. Second, we will determine whether there is selective sensitivity to therapy among specific founding clones and/or subclones. Third, we will investigate somatic mutation patterns that are associated with disease progression. Additional laboratory studies will be performed to characterize the functional consequences of aurora kinase inhibition on leukemic blasts during treatment.

## 2.5 Hypothesis

The addition of alisertib to "7+3" induction chemotherapy will enhance the rate of remission and other clinical outcomes in patients with high-risk acute myeloid leukemia.

#### 3. PARTICIPANT SELECTION

## 3.1 Eligibility Criteria

- 3.1.1 Participants must have pathologically confirmed, newly diagnosed high-risk acute myeloid leukemia, as defined by at least one of the following criteria
  - A. Age ≥65 years
  - B. Age ≥ 18 years with adverse risk karyotype, as per European Leukemia Net Guidelines (See Addendum B)
  - C. Age ≥ 18 years with antecedent or underlying myelodysplastic syndrome, CMML, or myeloproliferative neoplasm
  - D. Age  $\geq$  18 years with AML with MDS-related changes

#### \*\*Note:

For patients in category A, a sample to evaluate patient cytogenetics will be sent at the time of diagnosis per standard clinical care and the absence of favorable risk cytogenetics must be confirmed by Day 8. If the cytogenetic analysis reveals that the patient harbors favorable risk cytogenetics, or if the cytogenetic results are not received prior to Day 8, the participant will be removed from the study. Patients removed due to presence of favorable cytogenetics would be considered to be inevaluable and will be replaced. In addition, patients who receive less than half of their total alisertib dose during induction would be considered to be inevaluable and will be replaced.

3.1.2 Adults, age 18 years or older at the time of diagnosis, eligible for standard induction chemotherapy according to their treating physician, who fulfill criteria in section 3.1.1.

- 3.1.3 ECOG performance status 0-2 (Karnofsky ≥60%, see Appendix A)
- 3.1.4 Left ventricular ejection fraction > 50% as measured by echocardiogram or MUGA scan
- 3.1.5 Must not have received systemic antineoplastic therapy including radiation therapy within 14 days of the study enrollment, except hydroxyurea or 6-mercaptopurine for the purposes of cytoreduction. Patients may also have received *all-trans* retinoic acid (ATRA) if there is an early suspicion of acute promyelocytic leukemia (APL, M3-AML), although if confirmed to have APL these patients will be excluded from the study.
- 3.1.6 Adequate renal function as defined by: calculated creatinine clearance ≥ 40 mL/min (Cockcroft-Gualt Forumla)
- 3.1.7 Direct bilirubin < 2.0 x upper limit of nomal (ULN), SGOT (AST) and SGPT (ALT) < 2.5 x ULN. AST and/or ALT may be up to 5X ULN if thought to be secondary to leukemia.
- 3.1.8 The effects of alisertib on the developing human fetus are unknown. For this reason and because other chemotherapeutic agents are known to be teratogenic, women of child-bearing potential and men must agree to use adequate contraception (hormonal or barrier method of birth control; abstinence) prior to study entry and for the duration of study participation. Should a woman become pregnant or suspect she is pregnant while she or her partner is participating in this study, she should inform her treating physician immediately. Men treated or enrolled on this protocol must also agree to use adequate contraception for the duration of study participation, and 6 months after completion of therapy.
- 3.1.9 Subject must be able to take oral medication and to maintain a fast as required for 2 hours before and 1 hour after alisertib administration.
- 3.1.10 Ability to understand and the willingness to sign a written informed consent document.

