#### 5.2.3 Treatment with Alisertib

During Induction, treatment with alisertib will be as follows:

-Alisertib 30mg twice daily (every 12 hours) will be given on days 8-14 or 9-15

Alisertib will be begin on day 8, after the conclusion of "7+3" induction course. The exception would be if 7+3 therapy begins in the afternoon or evening, and therefore finishes late on day 8, in which case the first dose of Alisertib may be given on Day 9,

If "5+2" re-induction is administered, alisertib will not be given during this re-induction.

During Consolidation, treatment with Alisertib will be as follows: -Alisertib at 30mg PO twice daily (every 12 hours) will be administered for days 6-12 at after the conclusion of Cytarabine. Please note . if dose reduction took place for alisertib-related toxicity during induction, that dose-reduced dose will also be used during consolidation and subsequent maintenance

Following count recovery after induction and/or consolidation course(s), maintenance cycles of alisertib will be started and continued for 12 cycles, or until disease progression or unacceptable toxicity. Alisertib delays and dose modification are detailed in Section 6.

During Maintenance, treatment with Alisertib will be as follows:

- Alisertib 30mg PO twice daily (every 12 hours) will be administered for days 1-7 followed

by 14 days off, in 21 day cycles.

Subjects must be fasting for 2 hours before and 1 hour after Alisertib (MLN8237) administration. Only water is allowed during the fasting period. Subjects should take Alisertib within 3 hours of a missed dose. If more than 3 hours have passed, then that dose should be omitted, and the subject should resume treatment with the next scheduled dose. Vomited or missed doses of Alisertib will not be made up or re-dosed on this study.

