## **5.2.4 Remission Bone Marrow Aspiration and Biopsy**

Upon a peripheral blood count recovery of ANC of at least  $1000/\mu L$  and a platelet count of at least  $100,000/\mu L$ , following course of induction (and re-induction, if necessary) chemotherapy, a bone marrow aspirate and/or biopsy will be performed to assess and document response to therapy. A bone marrow aspirate and/or biopsy will also be performed if hematologic recovery has not occurred by day 42 (Range 35-45) (or day 63 if 5+2 re-induction was given based on day 14 bone marrow biopsy, range 55-65), or at any time that AML regeneration is suspected.

Response criteria will be as defined by modified International Working Group (IWG) as per Cheson et al [68]. If patient is found to have persistent AML, he/she will be discontinued from the study and proceed with additional management off-study per discretion of the treating oncologist.

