## 5.4 **Duration of Therapy**

In the absence of disease progression or unacceptable adverse event, alisertib will be continued for a period of up to 12 cycles of maintenance, based on the schedule above.

In the absence of treatment delays due to adverse events, treatment may continue as above until one of the following criteria applies:

- Disease progression,
- Intercurrent illness that prevents further administration of treatment,
- Unacceptable adverse event(s)
- Patient decides to withdraw from the study, or
- General or specific changes in the patient's condition render the patient unacceptable for further treatment in the judgment of the investigator.
- Patient becomes pregnant or begins breast-feeding
- Failure to return for follow-up

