#### 5.6 Criteria for Removal from Study

Patients will be removed from study when any of the criteria listed in **Section 5.4** applies, or if the study physician determines they cannot comply with the protocol. The reason for study removal and the date the patient was removed will be documented in the Case Report Form (CRF). Alternative care options will be discussed with the participant. In the event of unusual or lifethreatening complications, participating investigators must immediately notify the Principal Investigator, [name] MD, [name].

A QACT Treatment Ended/Off Study Form will be filled out when a participant comes off study. This form can be found on the QACT website or obtained from the QACT registration staff.

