## 7.3 Adverse Events Associated with Idarubicin and Cytarabine

Please refer to the appropriate package inserts for the comprehensive list of adverse events for each agent.

**Idarubicin:** Toxicities includes myelosuppression and cardiotoxicity. Cumulative dose beyond approximately 150 mg/m² (and equivalent cumulative doses with other anthracyclines) results in increased risk for myocardial injury, and congestive heart failure. Radiation therapy involving the heart and previous anthracycline administration increases the risk for cardiomyopathy. Hepatic and renal dysfunction may occur. Other reactions include reversible alopecia, nausea and vomiting, anorexia, diarrhea and mucositis. If extravasation occurs during administration, tissue necrosis can result. Rarely, chills, fever, skin rash and anaphylactoid reactions can occur. The occurrence of secondary acute leukemia has been reported rarely in patients treated with anthracycline chemotherapy.

Cytarabine: Toxicities include myelosuppression, nausea, vomiting, diarrhea, anorexia, anal ulceration, stomatitis, rash, headache, fever, myalgia, malaise, bone pain, chest pain, hepatic and renal dysfunction, and alopecia. Central nervous system toxicity, i.e., significant cerebral and cerebellar, dysfunction, progression to coma, has been seen with high doses, such as those given in consolidation. Severe cardiomyopathy has been reported with high dose Ara-C in combination with cyclophosphamide. Progressive ascending paralysis has occurred in two patients receiving IV and intrathecal ara-C. Marked keratoconjunctivitis has also occurred with high doses. Ara-C

can cause fetal harm when administered to a pregnant woman; however, there are no adequate and well-controlled studies in pregnant women.

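### Section 3.1.8 requires contraception of men for 6 months after therapy but states no post-therapy period for women of child-bearing potential

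*Combined protocol and SAP*

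**What the plan says.** Section 3.1.8 starts from the unknown effect of alisertib on the fetus and the known teratogenicity of the other chemotherapy. From that it sets one rule for women of child-bearing potential and men together: adequate contraception "prior to study entry and for the duration of study participation". A later sentence in the same item, addressed to men only, asks for contraception "for the duration of study participation, and 6 months after completion of therapy".

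Section 7.3 adds that cytarabine "can cause fetal harm when administered to a pregnant woman".

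Several sections describe how a patient leaves the study:

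- Section 5.2.4 discontinues patients with persistent AML, who are then managed off study.
- Section 5.2.5 lets patients come off study for transplant or another post-remission strategy.
- Section 5.6 states: "Patients will be removed from study when any of the criteria listed in" section 5.4. That list includes "Patient decides to withdraw from the study" and unacceptable adverse events.

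Section 5.5 then follows everyone for 30 days after removal. It also provides for contact at least every 3 months, for up to 12 months, to collect disease and survival status.

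**The concern.** The plan recognises that the reproductive risk outlasts treatment, because it binds men for 6 months after therapy. It gives no reason for stopping short of that in women, and its stated rationale does not separate the sexes. Women are left with a duty tied to a term that the protocol never defines.

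A site that takes participation to end at removal from study could tell a woman that her obligation under the protocol has ended while a man treated on the same dates is still bound. What is at stake is avoidable fetal exposure risk after therapy that the plan itself calls teratogenic. No statistical quantity is involved.

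**Working it through.** There is no figure to reproduce, so the check is a comparison of text.

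**Step 1: the two rules in 3.1.8.**

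| | Before entry | During participation | After therapy |
|---|---|---|---|
| Men | Yes | Yes | 6 months |
| Women of child-bearing potential | Yes | Yes | None stated |

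**Step 2: does another section supply the missing entry?**

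- 3.2.20 excludes pregnancy at screening and advises against breastfeeding.
- 5.4 stops treatment if "Patient becomes pregnant or begins breast-feeding".
- 7.5.1.1 requires drug-related serious events to be reported even after the follow-up period.
- 7.5.1.3 covers pregnancies arising while a woman is participating.
- The section 12 calendar lists a pregnancy test at baseline only.

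These are screening, stopping, reporting and testing rules. None requires contraception after the last dose.

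**Step 3: could study participation cover the period anyway?** Three readings are open.

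1. *It ends on removal from study.* Withdrawal or toxicity can lead to removal at any time, so the duty can end well short of 6 months after the last dose.
2. *It includes the 30 days after removal in 5.5.* For this to reach 6 months after the last dose, removal would have to come at least 6 months minus 30 days after that dose, which is about 5 months. Nothing in the protocol ensures that.
3. *It includes the contacts for up to 12 months in 5.5.* The duty could then equal or exceed the men's 6 months. But the contacts run up to 12 months, with study closure as an earlier end point, so no minimum is guaranteed.

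**Step 4: which reading does the wording favour?** For men, 3.1.8 names the time after therapy separately from participation. If participation always lasted at least 6 months beyond therapy, that addition would have no effect. Section 5.5 likewise speaks of follow-up after removal from the study. Both favour a narrower reading, but neither settles the matter. For a woman who completes all 12 maintenance cycles, the protocol does not say when participation ends.

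**The case against.** The strongest reply is that this is an undefined term rather than a plain omission. Under the third reading above, a woman's duty could match or exceed the man's. That stands as a limit on the claim: the text permits an early end to the duty but does not require one. It does not remove the need for a fix, because a commitment that a patient accepts at entry should not depend on which reading a site adopts.

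The documents also offer no direct evidence for a particular length in women. The cytarabine statement in 7.3 concerns exposure during pregnancy, and 2.1.4 gives alisertib a mean half-life of about 20 to 21 hours. Both points are fair. But the half-life covers only one of the drugs, and the plan adopts 6 months for men despite it. Women who leave for persistent AML or transplant will usually remain under specialist care, which lowers the practical risk without setting a rule.

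A reader might infer three stronger things that the documents do not support:

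- **That women in the trial received no instruction for the time after therapy.** The consent pages are not part of the public text and may give one. Only the silence of the protocol can be asserted.
- **That the gap can be stated as a number of days.** One might subtract the alisertib days in 5.2.3 from the marrow window in 5.2.4. That would describe the shortest reading of a single route, and the protocol does not fix when participation ends.
- **That pregnancy screening is also defective**, because the calendar accepts a serum or urine test while 3.2.20 requires serum. Section 3.2.20 is mandatory, and the eligibility check in 4.2 already controls registration.

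**Conclusion.** The concern holds as an unexplained asymmetry in 3.1.8. Men have a stated 6 months after therapy. Women of child-bearing potential have none, and the term that bounds their duty can be read to end when they come off study.

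The conclusion rests on the protocol text alone and on the absence of a definition of participation. The number of women concerned is not given. It may be small, since age 65 or over is by itself a qualifying criterion (3.1.1 A), although criteria B to D admit patients from age 18.

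This is a cheap improvement for patient safety. The primary endpoint, the two-stage design, the sample size and the error rates are unaffected.

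**What to change.** Amend 3.1.8 so that women of child-bearing potential, like men, must use adequate contraception during therapy and for at least 6 months after the last dose of any study therapy, whether or not they have come off study by then. Six months is the protocol's own figure for men. It should be lengthened if the drug labels or the investigator's brochure require more. Check that the consent form says the same.

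The cost is one sentence in the protocol and a matching check of the consent form, with no added visit or test. The downside is a possibly longer contraception commitment for what may be few women.
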